Secondary Objective(s):	
 
•To explore the association of the fecal calprotectin assessment regarding clinical and endoscopic outcomes.
 
•To explore the association of fecal calprotectin levels with clinical outcome throughout a follow up period of 96 weeks.
 
•To explore the association of fecal calprotectin levels with endoscopic activity throughout a follow up period of 96 weeks.
 
•To evaluate the impact of azathioprine in inducing clinical remission at week 12.
 
•Among patients who achieve clinical remission with azathioprine, to evaluate the maintenance of clinical remission up to week 96.
 
•To evaluate the impact of azathioprine in inducing endoscopic remission at week 96.
 
•To evaluate the impact of azathioprine in maintaining endoscopic remission throughout a follow up period of 96 weeks.
 
•To evaluate the rate of azathioprine persistence throughout a follow up period of 96 weeks
 

	
 
•To evaluate the time until loss clinical remission
 

Study Design:	
Multicenter, prospective, observational study designed to gather and analyze data on a consecutive cohort of subjects with CD who initiated therapy with azathioprine, according to physician's clinical decision. There is no imposed experimental intervention and prescribing decisions from the study physicians will be independent of patient's participation in this study.
 
The maximum overall duration of observation for each patient is 96 weeks since the start of observation period (Day 1).

Inclusion Criteria:	
Study patients must fulfill the following criteria:
 
 
1. Male or female patients, <18 years;
 
2. Patients who are registered in the GEDII Registry;
 
3. Patients who have been treated with exclusive polymeric diet and start azathioprine at diagnosis
 
 
AND who meet one of the following:
 
 
o Moderate/Severe disease (PCDAI>31) at start of study with fecal calprotectin levels > 100 ug/g
 
o Mild disease (PCDAI>11<30) with fecal calprotectin levels > 100 ug/g and/or Endoscopic activity (Simple endoscopic score for Crohn's disease [SES-CD] ≥ 3)
 
 
 
4. Patients who gave their informed consent.
 

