## 9 ENDPOINTS

### 9.1 PRIMARY ENDPOINT

- Proportion of patients who achieve fecal calprotectin remission (< 200 ug/g) at week 12.
- Proportion of patients who maintain fecal calprotectin remission (< 200 ug/g) at week 48 and 96.
- Proportion of patients who maintain fecal calprotectin remission (< 200 ug/g) at each data collection time point up to week 96.

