## **10 STATISTICAL ANALYSIS**

### **10.1 GENERAL CONSIDERATIONS**

All quantitative variables will be summarized through descriptive statistics namely mean, median, standard deviation and range (minimum and maximum) and qualitative variables through absolute (n) and relative frequencies (%) and 95% confidence intervals (if applicable). The statistical analysis will be performed through frequency tables for qualitative variables and tables with descriptive statistics for quantitative variables.

The association between two quantitative variables will be performed through Pearson correlation coefficient or Spearman correlation coefficient, in case the normality assumption is not verified.

The association of two categorical variables will be tested through the Chi-Square test or Fisher Exact test (if applicable).

The comparison of two independent samples in respect to quantitative variables will be performed through t-test for independent samples or the Mann-Whitney non-parametric test, according to the assumption validations of the statistical test (if applicable).

The proportion of patients with clinical (PCDAI), endoscopic (SES-CD) and biomarker remission (fecal calprotectin < 200 ug/g) at each data collection time points will be summarized using 95% confidence intervals, for the overall population and for the subset of patients with active and non-active CD at study inclusion.

Results for hemoglobin, leukocytes, neutrophils, eosinophiles, basophiles, monocytes, lymphocytes, erythrocyte sedimentation rate, CRP, ferritin, iron, transferrin and fecal calprotectin (Quantum Blue), will be summarized by total number of observations (n), mean, median, standard deviation, minimum and maximum.

The correlation between fecal calprotectin levels with clinical (PCDAI) and endoscopic (SES-CD) activity of disease will be analyzed through the Pearson or Spearman (in case the normality assumption is not verified) correlation coefficient at each data collection time point:

- Fecal calprotectin levels will be correlated with PCDAI score – Day 1, week 8 and every 12 weeks up to week 96.
- Fecal calprotectin levels will be correlated with Simple endoscopic score for Crohn's disease (SES-CD) – Day 1, and Week 96.

Generalized Estimated Equations will be used to investigate clinical and endoscopic remission (homogeneity) throughout data collection time points (time-effect) for each of the two subsets (patients with severe/moderate CD; patients with mild CD at Day 1).

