## **10.2 SAMPLE SIZE**

It is expected to analyze a total of 80 new patients. This sample size will allow the evaluation of the potential of fecal calprotectin in predicting the induction and maintenance of clinical and endoscopic remission in this population. Regarding the correlation analysis, with this sample size there is a power probability greater than 95% that the lower limit of a one-sided 95% confidence interval is higher than 0.50, if the observed correlation coefficient is at least 0.75.

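### Maintenance of calprotectin remission is a primary endpoint, but the only analysis stated for calprotectin remission is visit-wise prevalence, which may lie above or below maintenance

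*Protocol*

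**What the plan says.** Section 9.1 (and the synopsis) lists three primary endpoints and uses two verbs. The first is "Proportion of patients who achieve fecal calprotectin remission (< 200 ug/g) at week 12". The second is "Proportion of patients who maintain fecal calprotectin remission (< 200 ug/g) at week 48 and 96". The third is "Proportion of patients who maintain fecal calprotectin remission (< 200 ug/g) at each data collection time point up to week 96". Section 3.1 makes the same split between inducing remission at week 12 and maintaining it afterwards. Section 2.4 gives maintenance of calprotectin remission as the primary aim.

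Section 9.1 gives no denominator or anchor visit for the two maintenance endpoints, and Section 9.3 does not define calprotectin maintenance.

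Section 10.1 (and the synopsis) states one analysis of calprotectin remission: "biomarker remission (fecal calprotectin < 200 ug/g) at each data collection time points will be summarized using 95% confidence intervals, for the overall population", and also for subsets by disease activity at inclusion. The generalized estimating equations in 10.1 cover clinical and endoscopic remission only.

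Elsewhere the protocol sometimes conditions maintenance on earlier remission. The synopsis has this secondary objective: "Among patients who achieve clinical remission with azathioprine, to evaluate the maintenance of clinical remission up to week 96".

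**The concern.** Maintenance is a within-patient quantity: a patient must first be in remission and then stay there. A visit-wise proportion in the whole cohort does not follow patients from one visit to the next. It differs from maintenance in three ways:

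- a patient above 200 ug/g at week 12 and below it at week 96 enters the week-96 numerator;
- so does a patient who lost remission and regained it;
- a patient who never reached remission stays in the denominator.

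A flat curve of visit-wise proportions could come from stable remission or from steady turnover between patients, and the stated analysis cannot tell these apart. The primary aim of the study would then rest on a figure that does not answer it.

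The wording also leaves two choices open. Weeks 48 and 96 can mean each visit or both, and each time point can mean visit by visit or all visits together.

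**Working it through.** **The plan's own figure.** Section 10.2 gives one sample-size statement. It says "It is expected to analyze a total of 80 new patients", and its claim is "power probability greater than 95% that the lower limit of a one-sided 95% confidence interval is higher than 0.50". The claim supposes a correlation of 0.75 or more. With Fisher's z: (atanh 0.75 − atanh 0.50) × √(80 − 3) − 1.645 = 0.4236 × 8.775 − 1.645 = 2.07, so power is 0.981. The claim reproduces, but it concerns a correlation and says nothing about the maintenance endpoints.

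**Inputs for the illustration.** N = 80 is from Section 10.2. The protocol gives no calprotectin remission rates, so the rest is assumed, with no missing data:

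- p, in remission at week 12: 50 to 70%, central 60%.
- k, share of those in remission at the later visit: 40 to 60%, central 50%. This mirrors the 40 to 60% relapse on azathioprine quoted in Section 2.1, which is not a calprotectin rate.
- l, share of the others in remission at the later visit: 10 to 40%, central 20%.

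**Central case.** R = 0.60 × 80 = 48 in remission at week 12. K = 0.50 × 48 = 24 of them in remission later. L = 0.20 × 32 = 6.4, taken as 6 late remitters.

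| Quantity | Calculation | Result | Wilson 95% CI |
|---|---|---|---|
| Prevalence, as in 10.1 | (24 + 6)/80 | 37.5% | 27.7 to 48.5% |
| Maintenance among week-12 remitters | 24/48 | 50.0% | 36.4 to 63.6% |
| Achieved and maintained, out of all | 24/80 | 30.0% | 21.1 to 40.8% |

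Of the 30 patients in the prevalence numerator, 6 (20%) were not in remission at week 12.

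**Direction.** Prevalence minus conditional maintenance is pk + (1 − p)l − k = (1 − p)(l − k). At a single later visit, prevalence is the lower figure whenever week-12 remitters do better than the others (k > l). Over the assumed range it runs from 25 points below K/R to about 1 point above, the latter from rounding to whole patients. Against K/80 it is always higher, by L/80 = 2.5 to 20 points.

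**Remission at every visit.** Weeks 12 to 96 span 7 intervals. Assume prevalence constant at 60%, loss probability q per interval, gain probability g = 1.5q to balance it, and no memory:

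| | q = 0.04 | q = 0.08 | q = 0.15 |
|---|---|---|---|
| Prevalence at week 96 (by construction) | 60% | 60% | 60% |
| Week-96 remission among week-12 remitters, 0.6 + 0.4(1 − q − g)^7 | 79% | 68% | 61% |
| Remission at every visit among week-12 remitters, (1 − q)^7 | 75% | 56% | 32% |
| Remission at both week 48 and week 96, all patients, 0.6[0.6 + 0.4(1 − q − g)^4] | 52% | 46% | 40% |

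Prevalence is below every-visit maintenance in the first column and above it in the other two.

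**The case against.** **A stronger reading that a reader might infer.** One could say that the plan counts patients never in remission at week 12 as maintaining it, and so inflates the result. The documents do not support this. Section 10.1 never uses the word maintain, does not refer to the endpoints of 9.1, and nowhere says that late remitters count. Prevalence is simply the only analysis stated. Nor is the error one-sided: in the central case prevalence is below conditional maintenance.

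**Endpoint 3.** On a visit-by-visit reading, the third endpoint and 10.1 match almost word for word. That stands. The clash there is with the third primary objective in 3.1, which speaks of the whole follow-up.

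**Whether maintenance is conditional.** The protocol is not consistent. The synopsis objective quoted above is conditional, but its counterpart in 3.2 is not. Section 9.2 conditions time to loss of remission on earlier remission for moderate/severe disease but not for mild disease. The documents do not settle the denominator.

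**The anchor.** Week 12 follows naturally from the first endpoint, but the protocol never names it. The hypothesis in 2.5 refers to remission induced by diet, and the synopsis hypothesis is to achieve and maintain, which suggests a denominator of all patients. Stool is also sampled on Day 1 and at week 8.

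**Left to the SAP.** A SAP may define the responder rules. But the protocol fixes a maintenance endpoint in one section and a prevalence estimate with its population in another, and a SAP that follows 10.1 would inherit the mismatch.

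**The illustrations.** All rates are assumed. The 60% in every column of the second table is built in by the constant prevalence.

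**Conclusion.** The point holds as a mismatch between endpoint and analysis. Followed as written, the plan reports the prevalence of calprotectin remission, and this cannot answer the primary aim of maintenance. It is not a demonstrated plan to misclassify patients, and no direction of bias can be claimed.

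The size depends on rates that the protocol does not give. In the central case three defensible readings of the same data give 30%, 37.5% and 50%. These figures assume complete data. Section 6.3 allows observation to stop when azathioprine stops, so fewer than 80 patients may be observed at week 96.

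This should be fixed, but it does not endanger the study. The cohort is single-arm and descriptive, no test on these endpoints is stated, and calprotectin is sampled at every visit, so each version can be tabulated from the same data. The reason to settle it beforehand is that the definition should not be chosen once the results are known.

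**What to change.** In Sections 9.1 and 10.1, and in the synopsis:

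- State the anchor visit for maintenance. Week 12 follows from the first primary endpoint; reconcile it with the diet-induced remission in the hypothesis.
- Say whether weeks 48 and 96, and each time point, mean each visit or all visits together.
- Report with 95% CI the proportion below 200 ug/g at week 48, at week 96, at both, and at every sample from the anchor to week 96. Give each in two forms: among patients in remission at the anchor, and as achieved and maintained out of all patients.
- Keep the visit-wise proportions and label them as prevalence.

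The cost is wording and a few extra tables from samples already in the chronogram. The conditional estimate is less precise. If 48 of 80 patients are in remission at week 12, the interval widens by √(80/48) = 1.29, about 29%. With half-width 1.96 × √(P(1 − P)/n), where P is the observed proportion, that is about 14 against 11 points at P = 50%, and about 11 against 9 at P = 80%. The version out of all patients keeps the full denominator.

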### 9.2 SECONDARY ENDPOINTS

- **Fecal calprotectin** levels assessed at each data collection time point.
- **Fecal calprotectin** levels and **clinical activity (PCDAI)** at each data collection time point.
- **Fecal calprotectin** levels and **endoscopic activity (Simple endoscopic score for Crohn's disease [SES-CD])** at week 96.
- Proportion of patients with **clinical remission** (PCDAI<10) at each data collection time up to week 96.
- Proportion of patients who achieve **endoscopic remission** (SES-CD ≤ 2) at week 96.
- Proportion of patients on treatment with **azathioprine** at each data collection time point up to week 96.

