## 6 STUDY POPULATION

### 6.1 INCLUSION CRITERIA

Study patients must fulfill the following criteria:

1. Male or female patients, <18 years old
2. Patients who are registered in the GEDII Registry;
3. Patients who induce remission with polymeric diet and start azathioprine at diagnosis

**AND** who meet one of the following:

- o Moderate/Severe disease (PCDAI>30) at start of study
- o Mild disease (PCDAI<30) with fecal calprotectin levels > 100 ug/g and/or Endoscopic activity (Simple endoscopic score for Crohn's disease [SES-CD] ≥ 3

4. Patients who gave their informed consent.

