#### **Endoscopic activity**

- Endoscopic remission: SES-CD  $\leq 2$ .
- Endoscopic activity: SES-CD > 2 (3–6 as mildly active disease, 7–15 as moderately active disease and  $\geq 16$  as severely active disease).

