### **Simple endoscopic score for Crohn's disease (SES-CD)**

The SES-CD includes four variables: ulcer size, the extent of ulcerated surface, extent of affected surface, and stenosis, from 0 to 3 in five segments of the bowel. The scale can be assessed at: [http://www.gedii.pt/\\_scores\\_online](http://www.gedii.pt/_scores_online)

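### The week-96 endoscopic remission endpoint has no Day-1 SES-CD condition, so patients who enter already at SES-CD ≤ 2 and stay there are counted as having achieved remission

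*Protocol*

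**What the plan says.** The endpoint in section 9.2, repeated in the synopsis, is "Proportion of patients who achieve endoscopic remission (SES-CD ≤ 2) at week 96". Section 9.3 takes SES-CD ≤ 2 as remission and anything above as activity: "Endoscopic activity: SES-CD > 2 (3–6 as mildly active disease".

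Section 6.1 offers three ways in:

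- Moderate/severe disease: "Moderate/Severe disease (PCDAI>30) at start of study". The synopsis adds a biomarker condition, "at start of study with fecal calprotectin levels > 100 ug/g", but no SES-CD condition.
- Mild disease with raised calprotectin. The wording "with fecal calprotectin levels > 100 ug/g and/or Endoscopic activity" makes calprotectin sufficient alone.
- Mild disease with endoscopic activity: "and/or Endoscopic activity (Simple endoscopic score for Crohn's disease [SES-CD] ≥ 3".

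Only the third route depends on the SES-CD.

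The objectives differ on what is measured at week 96. The synopsis has "To evaluate the impact of azathioprine in inducing endoscopic remission at week 96"; the matching line in section 3.2 speaks of maintaining remission. Both lists also carry an objective of maintaining endoscopic remission over the 96 weeks.

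The chronogram schedules colonoscopy with SES-CD at Day 1 and at week 96 (or discontinuation). Section 10.1 plans remission proportions with 95% confidence intervals at each time point, overall and by active or non-active CD at inclusion. It also plans generalised estimating equations for remission over time, separately for moderate/severe and mild CD.

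**The concern.** To achieve remission, a patient has to start outside it. The endpoint counts everyone at SES-CD ≤ 2 at week 96 whatever the starting score, and the entry criteria admit patients who start at 0, 1 or 2. For those patients an unchanged score is a success.

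The protocol itself makes such patients plausible. Section 2.1 describes a disease that can involve any part of the gastrointestinal tract, while the SES-CD scores items "from 0 to 3 in five segments of the bowel", so disease elsewhere can raise the PCDAI with little endoscopic score. The calprotectin entry cut-off (above 100 µg/g) also lies below the study's own biomarker remission cut-off (below 200 µg/g), so a mild patient can enter on a value that already counts as biomarker remission, with no SES-CD condition.

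At stake is the meaning of the only endoscopic remission proportion among the endpoints. Induction concerns patients who start at ≥ 3, and maintenance concerns those who start at ≤ 2. One proportion over all patients measures neither.

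**Working it through.** **The plan's own figure.** The protocol gives no sample-size or precision figure for endoscopic remission. Its one calculation (section 10.2) concerns the correlation analysis. Taking 0.75 as the true correlation and n = 80, Fisher's z gives power = Φ[(atanh 0.75 − atanh 0.50)·√77 − 1.645] = 98.1%, in agreement with the stated figure of more than 95%. This neither supports nor weakens the present point.

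**Inputs.**

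- n = 80 (section 10.2).
- p, the remission rate among patients with Day-1 SES-CD ≥ 3: not given. For illustration, the two adult mucosal-healing figures in section 2.1, 16.5% and 58%.
- f, the share with Day-1 SES-CD ≤ 2: not given. Assumed 5–30%.
- s, the share of those still at ≤ 2 at week 96: not given. Assumed 80% or 100%.

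**Formula.** Reported proportion = f·s + (1 − f)·p. Its difference from p is f·(s − p), which is positive whenever s exceeds p.

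**Example.** With f = 0.20, s = 0.80 and p = 0.165: 0.20 × 0.80 + 0.80 × 0.165 = 0.160 + 0.132 = 29.2%. The excess is 0.20 × (0.80 − 0.165) = 12.7 percentage points.

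| f | Patients with Day-1 SES-CD ≥ 3 | p = 16.5%, s = 80% | p = 16.5%, s = 100% | p = 58%, s = 80% | p = 58%, s = 100% |
|---|---|---|---|---|---|
| 5% | 76 | 19.7% | 20.7% | 59.1% | 60.1% |
| 10% | 72 | 22.9% | 24.9% | 60.2% | 62.2% |
| 20% | 64 | 29.2% | 33.2% | 62.4% | 66.4% |
| 30% | 56 | 35.6% | 41.6% | 64.6% | 70.6% |

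The distortion is large when healing is uncommon and modest when it is common. In the limit p = 0 and s = 100%, nobody with lesions heals and the endpoint still reads f. Each patient who enters and stays at ≤ 2 contributes 1/80 = 1.25 percentage points.

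**In counts** (f = 20%, s = 100%, p = 16.5%, Wilson 95% intervals). Sixteen patients enter at ≤ 2 and stay there. Of the other 64, 64 × 0.165 ≈ 11 reach remission. As written, the endpoint is (16 + 11)/80 = 33.8% (24.3 to 44.6). Among patients who could achieve remission it is 11/64 = 17.2% (9.9 to 28.2).

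**Does a planned analysis separate the groups?** The moderate/severe and mild subsets rest on PCDAI (section 9.3). The active/non-active split is not defined, and the nearest definition of clinically active disease is again PCDAI. No analysis in section 10.1 is stated to be confined to Day-1 SES-CD ≥ 3.

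**The case against.** The best defence is that section 10.1 does not ignore baseline. It reports the remission proportion at each time point, so the Day-1 share already at ≤ 2 would stand beside the week-96 figure, and the generalised estimating equations compare the two visits. That stands in part: a reader would see f. It does not show which patients make up the week-96 figure, so neither p nor s can be recovered from the two marginal proportions. If the active/non-active split was meant to be by SES-CD, most of the point would be met, but the protocol does not say so.

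Second, under the section 3.2 wording, patients already in remission belong in the count. That is fair for a maintenance objective, but the denominator would then have to be those patients alone, and the synopsis says the opposite.

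Third, the size is assumed and may be small. Patients are newly diagnosed, and section 2.1 calls endoscopy mandatory for confirming the diagnosis, so many may enter with visible lesions. This stands. The entry criteria do not bound f.

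Stronger readings are tempting but not supported:

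- *That the entry cut-off (≥ 3) and the remission cut-off (≤ 2) lie too close together.* Section 9.3 defines activity and remission as complementary states, and on an integer scale these must meet at neighbouring values.
- *That the endpoint needs a minimum fall in score.* It is a remission state, not a response, and the documents give no basis for any particular fall.
- *That reading error alone inflates the result.* Over all patients, with no true change and the same reading error at both visits, the expected proportion at ≤ 2 is the same on Day 1 and at week 96. Inflation from that source arises after selecting on a high Day-1 reading, which the protocol's denominator does not do.

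**Conclusion.** The point holds for the denominator and the wording. Patients already at SES-CD ≤ 2 on Day 1 are eligible by two of three routes and, if they stay there, are reported as having achieved remission. A patient who enters at ≥ 3 and does not change is not counted, so it would be wrong to infer that unchanged patients in general are successes. The bias is not favourable by construction either: it has the sign of s − p.

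With f of 10–30% and s of 80%, a rate of 16.5% is reported as about 23–36%; with a rate of 58% the excess is 2 to 7 percentage points. All of this rests on assumed f and s and on adult healing rates used only as illustration. The endpoint is secondary, in an uncontrolled observational cohort, and can be repaired from data already scheduled. It is a cheap improvement worth making, and it does not threaten the primary result.

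**What to change.** In section 9.2 and the synopsis, replace the single proportion with:

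1. Achieved endoscopic remission: SES-CD ≤ 2 at week 96 among patients with Day-1 SES-CD ≥ 3.
2. Remained in endoscopic remission: SES-CD ≤ 2 at week 96 among patients with Day-1 SES-CD ≤ 2.
3. The all-patient proportion, as a supplementary figure.

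Reconcile the synopsis (inducing) with section 3.2 (maintaining) for week 96, tying each objective to its own proportion. In section 10.1, state whether the active/non-active split refers to PCDAI or SES-CD.

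No new data are needed. One cost is precision: at a rate near 16.5%, the 95% interval goes from 9.7–25.8% with 13/80 to 9.9–28.2% with 11/64. The other is that selecting on a single Day-1 reading brings some regression to the mean into the first proportion, so some patients will read ≤ 2 at week 96 without true change. The report should say so, and the supplementary all-patient figure, set beside its Day-1 counterpart, provides a check.
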